1.1 Objective(s)

The objectives of this study are as follows:

- To quantify and characterize the usage of the EnSite Precision™ Cardiac Mapping System (software version 2.0.1 or higher) modules
- To characterize the mapping duration and point usage when using multipolar catheters with the EnSite™ AutoMap module
- To characterize the relationship of the system usage to patient outcomes in a variety of electrophysiological (EP) procedures and clinical settings.

1.2 Devices Used

All devices must have proper regulatory clearance and will be used according to their Instructions for Use (IFU).

The following devices will be used in this clinical study:

Table 1: Identification of Clinical Study Devices

Device name	Model/Type	Manufacturer	Region/ Country	Investigational or Market Released
EnSite Precision™ Software	V2.0.1 or higher	SJM	Worldwide	Market Released
EnSite Precision™ Module, Sensor Enabled	H702473	SJM	Worldwide	Market Released
EnSite Precision™ Surface Electrode Kit	EN0020-P	SJM	Worldwide	Market Released
EnSite™ AutoMap Module	H702498	SJM	Worldwide	Market Released
AutoMark Module	V1.0	SJM	Worldwide	Market Released

Additional commercially available tools may be used in this clinical study, per physician's discretion and per their IFUs.

1.3 Indications for Use

The EnSite Precision™ Cardiac Mapping System is a catheter navigation and mapping system capable of displaying the three-dimensional (3D) position of conventional and sensor enabled electrophysiology catheters, as well as displaying cardiac electrical activity as waveform traces and as dynamic 3-D isopotential maps of the cardiac chamber. The contoured surfaces of these three-dimensional maps are based on the anatomy of the patient's own cardiac chamber.

The EnSite Precision™ Cardiac Mapping System (including AutoMap) is a suggested diagnostic tool in patients for whom electrophysiology studies have been indicated.

The EnSite Precision™ system interfaces to either MediGuide™ Guided Medical Positioning System or the EnSite Precision™ Module to combine and display magnetic processed patient positioning and orientation mapping information.

When used with compatible hardware, the AutoMark module is intended to automatically catalog and display various parameters associated with radiofrequency (RF) information on the 3D model in real-time.

1.4 Design

This is a prospective, multicenter, post-market, observational study designed to quantify and characterize the usage of the EnSite Precision™ Cardiac Mapping System in a real-world environment.

1.5 Endpoints

The endpoints for evaluating the objectives are as following:

- Summary of subjects that used EnSite™ AutoMap and AutoMark module
- Summary of EnSite™ Automap and AutoMark module software settings used per arrhythmia
- Assessment of EnSite™ AutoMap Module including:
 - o Mapping time associated with (re-)mapping one or multiple arrhythmias per catheter type used in a single subject
 - o Used Points per Minute per catheter type stratified by arrhythmia type and mapping type
- Rate of acute success based on pre-defined procedural endpoints
- Freedom from arrhythmia recurrence through 12 months
- Number of repeat ablations up to 12 months
- Summary of NavX patch placement locations used
- Number of gaps in lesions identified requiring touch-up ablation
- Changes in EQ-5D quality of life score at 6 and 12 months
- Number of unscheduled visits and hospitalizations due to arrhythmias
- Overall procedure time
- Overall system stability

1.6 Study Population

The intended population for this study is patients over the age of 18 years who are eligible for a cardiac EP mapping and RF ablation procedure using the EnSite Precision™ Cardiac Mapping.

1.7 Inclusion/Exclusion Criteria

1.7.1 Inclusion Criteria

To participate in this study, the subject must meet all of the following inclusion criteria:

- Indicated for a cardiac EP mapping and RF ablation procedure using a 3D mapping system per IFU
- Over 18 years of age
- Able to provide informed consent for study participation and willing and able to comply with the protocol described evaluations and follow up schedule

1.7.2 Exclusion Criteria

Subjects who meet any of the following exclusion criteria must be excluded from the study:

- Patients who are only presenting with:
 - o Atrioventricular Nodal Reentrant Tachycardia (AVNRT)

- Atrioventricular Reentrant Tachycardia (AVRT)
- Planned cryoablation procedure
- Implanted with a neurostimulator
- Contraindication to anticoagulation
- Known presence of cardiac thrombus
- Recent (<3 months) myocardial infarction or unstable angina or coronary artery by-pass
- Currently enrolled in a clinical study/investigation evaluating another device or drug that would confound the results of this study
- Pregnant or nursing
- Individuals whose willingness to volunteer in a study, in the judgement of investigator or public authorities, could be unduly influenced by lack of or loss of the autonomy due to immaturity, or mental disability, or adverse personal circumstances, or hierarchical influence

1.8 Enrollment

A subject is considered enrolled in the clinical study from the moment the subject has provided a written Informed Consent.

1.9 Study Assessments

Refer to Section 6, Procedures for the Clinical Study Procedures Table

2 Introduction

This document is a clinical investigation plan (CIP) for the EnSite Precision Observational Study. This clinical study is intended to quantify and characterize the usage of the EnSite Precision™ Cardiac Mapping System (Software version 2.0.1 or higher) in a real-world environment. This study will be conducted in patients who are indicated for a cardiac EP mapping and RF ablation procedure using a 3D system.

This document describes the rationale and procedures used for a prospective, multicenter, observational study. The clinical study is sponsored by St. Jude Medical / Abbott.

The clinical study will be conducted in accordance with this CIP. All parties involved in the conduct of the clinical study will be qualified by education, training, or experience to perform their tasks and this training will be documented appropriately.

3 Background and Justification for Clinical Study

Atrial fibrillation (AF) is a common cardiac rhythm disturbance and increases in prevalence with advancing age. Approximately 1% of patients with AF are <60 years of age, whereas up to 12% of patients are 75 to 84 years of age. More than one third of patients with AF are >80 years of age. In the United States, the percentage of Medicare Fee-for-Service beneficiaries with AF in 2010 was reported as 2% for those <65 years of age and 9% for those ≥ 65 years of age.

The mechanisms causing and sustaining AF are multifactorial, and can be complex and difficult for clinicians to manage (January, et al., 2014). Ablation is increasingly used for AF and is superior to pharmacological therapy for patients with early (paroxysmal) to advanced (persistent) AF (Wright & Narayan, 2015).

Sustained ventricular tachycardia (VT) and ventricular fibrillation (VF) are typically a manifestation of significant structural heart disease and often associated with a high risk of sudden cardiac death. Implantable cardioverter defibrillators (ICDs) remain the mainstay of therapy for prevention of sudden cardiac death associated with these arrhythmias. However, ICDs treat the arrhythmia after it occurs and does not prevent the arrhythmia. Recurrent ventricular arrhythmias can lead to multiple ICD shocks that are painful, decrease quality of life and cause post-traumatic stress disorder. Spontaneous VT and ICD shocks are also associated with an increased risk of death and progressive heart failure. Antiarrhythmic drugs, notably amiodarone, reduce arrhythmias for some patients, but have limited efficacy for long-term management, particularly for scar-related re-entrant arrhythmias. In addition, antiarrhythmic drugs have the potential for significant adverse effects that includes negative inotropy, pro-arrhythmia and non-cardiac organ toxicities that limit their long-term use. Catheter ablation offers an alternative therapy for preventing arrhythmias, and can be life-saving when frequent episodes (VT storm) threaten survival. (Nof, Stevenson, & John, 2013) (Pedersen, et al., 2014)

The incidence and treatment complexity of these arrhythmias represent an opportunity for the EnSite™ Velocity Cardiac Mapping System due to the increased case complexity and duration, as mapping system precision is a key requirement to maximize the success of these challenging procedures. As a result, the EnSite Precision™ System was developed to introduce features such as Delayed Enhancement Magnetic Resonance Imaging (DE-MRI) image integration, lesion marking automaticity, automatic mapping, and workflow flexibility to aid in the success of complex ablation procedures. This clinical study is intended to understand how the EnSite Precision™ System is utilized in the treatment of complex ablation procedures.

4 Devices Used

4.1 Identification and Description of the Clinical Study Devices

4.1.1 Identification

All of the devices used in this study, must have received proper regulatory clearance and must be market released.

The following devices will be used in this clinical study according to their IFU.

Table 2: Identification of Clinical Study Devices

Device name	Model/Type	Manufacturer	Region/ Country	Investigational or Market Released
EnSite Precision™ Software	V2.0.1 or higher	SJM	Worldwide	Market Released
EnSite Precision™ Module, Sensor Enabled	H702473	SJM	Worldwide	Market Released
EnSite Precision™ Surface Electrode Kit	EN0020-P	SJM	Worldwide	Market Released
EnSite™ AutoMap Module	H702498	SJM	Worldwide	Market Released
AutoMark Module	V1.0	SJM	Worldwide	Market Released

Additional commercially available tools may be used in this clinical study, per physician's discretion and per their IFUs.

4.1.2 Device Description and Intended Purpose

The EnSite Precision™ Cardiac Mapping System is a catheter navigation and mapping system capable of displaying the three-dimensional (3D) position of conventional and sensor enabled electrophysiology catheters, as well as displaying cardiac electrical activity as waveform traces and as dynamic 3-D isopotential maps of the cardiac chamber. The contoured surfaces of these three-dimensional maps are based on the anatomy of the patient's own cardiac chamber.

The EnSite Precision™ Cardiac Mapping System (including AutoMap) is a suggested diagnostic tool in patients for who electrophysiology studies have been indicated.

The EnSite Precision™ system interfaces with either MediGuide™ Guided Medical Positioning System or the EnSite Precision™ Module to combine and display magnetic processed patient positioning and orientation mapping information.

When used with compatible hardware, the AutoMark module is intended to automatically catalog and display various parameters associated with RF information on the 3D model in real-time.

[figure not shown]
4.1.3 Device Handling and Storage

Only commercially available shelf-stock will be used. All devices will be handled and stored per standard practice of the hospital.

5 Clinical Study Design

5.1 Clinical Study Design

This is a prospective, multicenter, post-market, observational study designed to quantify and characterize the usage of the EnSite Precision™ Cardiac Mapping System in a real-world environment.

5.2 Objectives

The objectives of this study are as follows:

- To quantify and characterize the usage of the EnSite Precision™ Cardiac Mapping System (software version 2.0.1 or higher) modules
- To characterize the mapping duration and point usage when using multipolar catheters with the EnSite™ AutoMap module
- To characterize the relationship of the system usage to patient outcomes in a variety of electrophysiological (EP) procedures and clinical settings.

5.3 Endpoints

The endpoints for evaluating the objectives are as following:

- Summary of subjects that used EnSite™ AutoMap and AutoMark module
- Summary of EnSite™ Automap and AutoMark module software settings used per arrhythmia
- Assessment of EnSite™ AutoMap Module including:
 - o Mapping time associated with (re-)mapping one or multiple arrhythmias per catheter type used in a single subject
 - o Used Points per Minute per catheter type stratified by arrhythmia type and mapping type
- Rate of acute success based on pre-defined procedural endpoints
- Freedom from arrhythmia recurrence through 12 months
- Number of repeat ablations up to 12 months
- Summary of NavX patch placement locations used
- Number of gaps in lesions identified requiring touch-up ablation
- Changes in EQ-5D quality of life score at 6 and 12 months
- Number of unscheduled visits and hospitalizations due to arrhythmias
- Overall procedure time
- Overall system stability

5.4 Study Population

The intended population for this clinical study is patients over the age of 18 years who are eligible for a cardiac EP mapping and RF ablation procedure using the EnSite Precision™ Cardiac Mapping System.

5.4.1 Inclusion Criteria

To participate in this clinical study, the subject must meet all of the following inclusion criteria:

- Indicated for a cardiac EP mapping and RF ablation procedure using a 3D mapping system per IFU
- Over 18 years of age
- Able to provide informed consent for study participation and willing and able to comply with the protocol described evaluations and follow up schedule

5.4.2 Exclusion Criteria

Subjects who meet any of the following exclusion criteria must be excluded from the clinical study:

- Patients who are only presenting with:
 - o Atrioventricular Nodal Reentrant Tachycardia (AVNRT)
 - o Atrioventricular Reentrant Tachycardia (AVRT)
- Planned cryoablation procedure
- Implanted with a neurostimulator
- Contraindication to anticoagulation
- Known presence of cardiac thrombus
- Recent (<3 months) myocardial infarction or unstable angina or coronary artery by-pass
- Currently enrolled in a clinical study/investigation evaluating another device or drug that would confound the results of this study
- Pregnant or nursing
- Individuals whose willingness to volunteer in a study, in the judgement of investigator or public authorities, could be unduly influenced by lack of or loss of the autonomy due to immaturity, or mental disability, or adverse personal circumstances, or hierarchical influence

6 Procedures

Approval from the Sponsor must be received prior to initiating study related activities.

Subjects will undergo a cardiac mapping and RF ablation procedure using the EnSite Precision™ Cardiac Mapping System per the IFUs of all devices used during the procedure. After the post-procedure hospital discharge, the subject will have 3 in-clinic visits: at 1 month, 6 months and 12 months post-procedure. Upon completion of the 12-month follow-up visit, the subject will be considered to have completed the follow-up requirements of this clinical study. The Principal Investigator should arrange for appropriate care of subjects following study completion.

The following sections provide a detailed description of procedures required by this CIP.

6.1 Informed Consent Process

The Principal Investigator or his/her authorized designee will conduct the informed consent process, as required by applicable regulations and the center's IRB/EC. This process will include a verbal discussion with the subject on all aspects of the clinical study that are relevant to the subject's decision to participate, such as details of clinical study procedures, anticipated benefits, and potential risks of clinical study participation. During the discussion, the Principal Investigator or his/her authorized designee will avoid any improper influence on the subject and will respect subject's legal rights. The subject shall be provided with the informed consent form (refer to Appendix F) written in a language that is understandable to the subject and has been approved by the center's IRB/EC. The subject shall have adequate time to review, ask questions and consider participation.

If the subject agrees to participate, the informed consent form must be signed and dated by the subject and by the person obtaining the consent. The signed original will be filed in the subject's hospital or research charts, and a copy will be provided to the subject.

The Principal Investigator or his/her authorized designee will document the informed consent process in the subject's hospital and/or research charts. The date of signature will be entered on an applicable Case Report Form (CRF).

Failure to obtain informed consent from a subject prior to a study specific procedure should be reported to Sponsor within 5 working days and to the reviewing center's IRB/EC according to the IRB's/ EC's reporting requirements.

If, during the clinical study, new information becomes available that can significantly affect a subject's future health and medical care, the Principal Investigator or his/her authorized designee will provide this information to the subject. If relevant, the subject will be asked to confirm their continuing informed consent in writing.

6.2 Point of Enrollment

A subject is considered enrolled in the clinical study from the moment the subject has provided a written Informed Consent.

6.3 Scheduled Procedures

The Principal Investigator is responsible for ensuring all clinical study data is collected as required per CIP scheduled procedures.

6.3.1 Baseline Visit (within 10 days from Informed Consent)

The following assessments and information will be collected at the baseline visit:

- Demographics - include subject's age and gender
- Physical information - include subject's height, weight (measurements taken during visit)
- Cardiac History (most recent value prior to baseline visit)
- Arrhythmia History
- 12 Lead ECG information (most recent information prior to baseline visit)
- Antiarrhythmic medication - indicate both the medication that failed and the medication (if any) the patient is currently taking
- Current anticoagulant medication
- Completion of the EQ-5D questionnaire (refer to Appendix H for additional information)

Record the required information on the Baseline form.

6.3.2 Procedure Visit (within 14 days from Baseline)

The procedure should be performed according to the IFU of the EnSite Precision™ Cardiac Mapping System, the IFUs of the AutoMark and EnSite™ AutoMap modules and any other medical devices used during the procedure.

Subjects will be prepared according to the standard ablation procedures and standard practice of the center.

The following information will be collected during the Procedure Visit:

- Mapping and ablation tools used during the procedure
- Procedural characteristics (set up and timing)
- AutoMap settings used (if applicable)
- AutoMark setting used (if applicable)
- Field Scaling used

Sponsor representatives can be involved in providing support during the procedure.

The entire case (procedure) should be recorded and stored on a study-specific USB (password-protected), provided by the Sponsor, and returned within reasonable timelines to the Sponsor.

A User Experience form should be completed once by every physician performing a procedure for this study, preferably after the first study related procedure performed by that physician.

Protocol deviations (refer to section 9.1 for details) that were observed during the procedure will also be recorded at this time.

NOTE: A separate guideline for additional information on supplementary data collection will be available. This guideline is not mandatory, however, it may assist in increasing knowledge and understanding of the treatment options for patient with arrhythmias.

6.3.3 Scheduled Follow-ups

In-clinic follow-up visits are scheduled at 1 month, 6 months and 12 months after procedure. The scheduled visit windows are calculated from the index procedure.

6.3.3.1 1-Month Visit (within 30 days from procedure)

The 1-month visit needs to be performed within 30 days post procedure, depending on the hospital's standard practice for 1st follow-up post procedure.

The following information is collected:

- Arrhythmia recurrence
 - o For the purpose of this clinical study, recurrence of arrhythmia is deemed to have occurred only when the arrhythmia is documented on ECG or during a period of monitoring e.g. holter-monitoring or implantable cardiac monitor. Atrial arrhythmias 30 seconds or longer will be collected. Ventricular arrhythmias treated by an ICD, or lasting 20 seconds or longer will be collected.
- Antiarrhythmic / Anticoagulant medication
- Healthcare Utilization information when applicable
- Protocol deviation, when applicable

6.3.3.2 6- and 12-Month Visit (\pm 30 days)

At each visit, the following information is collected:

- Arrhythmia recurrence
 - o For the purpose of this clinical study, recurrence of arrhythmia is deemed to have occurred only when the arrhythmia is documented on ECG or during a period of monitoring e.g. Holter-monitoring or implantable cardiac monitor. Atrial arrhythmias 30 seconds or longer will be collected. Ventricular arrhythmias treated by an ICD, or lasting 20 seconds or longer will be collected.
- Antiarrhythmic / Anticoagulant medication
- Completion of the EQ-5D questionnaire

- Holter monitoring* at 12-Month visit (for patients treated for AF)
- Healthcare Utilization information when applicable
- Protocol deviation, when applicable

***Holter Monitoring (AF only)**

Subjects with AF will be issued a holter monitor at the 12-month visit and instructed to obtain a 48-hour recording. A core laboratory will review each recording and report findings to the Sponsor.

NOTE: The Sponsor may request access to other patient data during the required protocol follow up visits or throughout the follow up period, which may include, but is not limited to, data from implanted device(s).

Record the required information on the appropriate CRF(s). Documentation of arrhythmia (e.g. ECG printouts, holter printouts, session records), where applicable, should be retrieved and submitted electronically through EDC to the Sponsor.

Sponsor representatives can be involved in providing support during the follow-up procedures.

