6.5 Study Flow Chart

The Study Flow Chart (fig. 1) and Table 3 below summarize subject flow and requirements of this clinical study.

Figure 1: Study Flow Chart

[figure not shown]

Table 3: List of all clinical study specific tests/activities and procedures

Study Activity	Visit	Enrollment	Baseline Visit (Max 10 days from Informed Consent)	Procedure Visit (Max 14 days after baseline)	1-month Visit (Within 30 days post procedure)	6-month Visit (± 30 days)	12-month Visit (± 30 days)
Eligibility check		X					
Informed Consent Process		X					
Demographics			X				
Physical information			X				
Cardiac History			X				
Arrhythmia History			X				
12 Lead ECG			X				
Antiarrhythmic / Anti-coagulant Medication			X		X	X	X
EQ-5D questionnaire			X			X	X
Mapping of cardiac structures				(X)			
RF Ablation				(X)			
User Experience				(X) ¹			
Obtain Procedure USB				X			
Arrhythmia Recurrence					(X)	(X)	(X)
48-hour Holter-monitoring (AF only)							(X) ²
Healthcare Utilization information					(X)	(X)	(X)
Deviation		(X)	(X)	(X)	(X)	(X)	(X)
Withdrawal		(X)	(X)	(X)	(X)	(X)	(X)

(X) If applicable

¹ Only required for first procedure performed by physician

² Only required for patients treated for AF

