Appendix C: Definitions

Non-study Specific Definitions

Vulnerable Subject

Vulnerable subject is defined as individual whose willingness to volunteer in a clinical investigation could be unduly influenced by the expectation, whether justified or not, of benefits associated with participation or of retaliatory response from senior members of a hierarchy in case of refusal to participate.

EXAMPLE Individuals with lack of or loss of autonomy due to immaturity or through mental disability, persons in nursing homes, children, impoverished persons, subjects in emergency situations, ethnic minority groups, homeless persons, nomads, refugees, and those incapable of giving informed consent. Other vulnerable subjects include, for example, members of a group with a hierarchical structure such as university students, subordinate hospital and laboratory personnel, employees of the Sponsor, members of the armed forces, and persons kept in detention.

Complaint

Any written, electronic or oral communication that alleges deficiencies related to the identity, quality, durability, reliability, safety, effectiveness or performance of a device after it is released for distribution.

Study Specific Definitions

Arrhythmia recurrence

For the purpose of this clinical study, recurrence of arrhythmia is deemed to have occurred only when the arrhythmia is documented on ECG or during a period of monitoring e.g. Holter-monitoring, implantable cardiac monitor, ICD, CRT... Atrial arrhythmias must be 30 seconds or longer. Ventricular arrhythmias are any treated by ICD or 20 seconds or longer.

Blanking period (AF only)

The 3-month (90 days) period of time following a procedure in which AF episodes can occur as part of the body's healing response. Any arrhythmia activity during that blanking period is not counted in the study's results and is not used in determining success or failure of the procedure.

Acute success

For the purpose of this study, acute success is attained when one (or multiple) predefined procedural endpoints, have been realized. These predefined procedural endpoints include, but are not limited to:

- Abolition of all clinical ventricular ectopies and unstable ventricular arrhythmias
- Bidirectional block across CTI
- Block across mitral isthmus
- Confirmation of vagal reflexes
- CS isolation
- Documentation of block at a critical isthmus of conduction
- Elimination and noninducibility of tachycardia following ablation
 - o With burst pacing

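### Freedom from recurrence counts only documented episodes, but little rhythm recording is scheduled, device data are retrieved at discretion, and unrecorded subjects count as event-free

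*Combined protocol and SAP*

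**What the plan says.** **Event.** Section 6.3.3 states that "recurrence of arrhythmia is deemed to have occurred only when the arrhythmia is documented on ECG or during a period of monitoring". Atrial episodes must last at least 30 seconds. For the ventricle, "Ventricular arrhythmias treated by an ICD, or lasting 20 seconds or longer will be collected". Appendix C repeats the rule and lists the qualifying sources as "Holter-monitoring, implantable cardiac monitor, ICD, CRT", so near-continuous device recording and short intermittent recording count alike.

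**Scheduled recording.** Table 3 in section 6.5 shows a 12-lead ECG at baseline only. After the procedure the one scheduled recording is the Holter described after section 6.3.3.2: "Subjects with AF will be issued a holter monitor at the 12-month visit and instructed to obtain a 48-hour recording". The Table 3 footnote reads "Only required for patients treated for AF". The 1-, 6- and 12-month visits collect arrhythmia recurrence if applicable, with no ECG or device interrogation required to look for it. Section 8 says that the study requires nothing beyond standard of care.

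**Device data.** The note on Holter monitoring says: "The Sponsor may request access to other patient data during the required protocol follow up visits or throughout the follow up period". It names implanted-device data as an example and gives no rule on whose data, when or why. The next paragraph asks sites to submit existing arrhythmia documentation, including session records, where applicable.

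**Analysis.** Section 7.1.1 specifies Kaplan-Meier from the index procedure. Subjects without an event are followed to death, withdrawal or last follow-up. AF events in the first 90 days are excluded. Section 7.1.4 plans no subgroup analysis, section 7.1.5 no imputation, and no sensitivity analysis by monitoring is described.

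**The concern.** A recurrence that nobody records is, for this endpoint, no recurrence. A subject with an implanted monitor, ICD or CRT device has far more chance of a recorded event than one seen in clinic three times in a year. The analysis treats the two alike: each contributes event-free time up to last follow-up, even if the second had no rhythm recording after discharge.

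Two things are at stake. The overall estimate of freedom is too high by an unknown amount. The error also differs between groups whose monitoring differs. The third objective in section 5.2 is to relate system usage to patient outcomes, and section 7.2 foresees recommendations for best practice from the results. If monitoring varies with center, arrhythmia or usage pattern, a difference in freedom can reflect detection alone.

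**Working it through.** The plan gives no recurrence rate, detection rate or device prevalence, so there is no figure of its own to reproduce. Steps 1 and 2 use the documents; steps 3 to 5 use labelled assumptions.

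**1. Coverage by scheduled recording.** One 48-hour Holter is 2 days.
- AF, whole year: 2/365 = 0.55%.
- AF, after the 90-day blanking period: 2/(365 - 90) = 2/275 = 0.73%.
- All other subjects: 0%.

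**2. Time at risk against time observed.** Section 7.1.1 ends event-free time at last follow-up, not at the last rhythm recording. A non-AF subject who attends all visits and is never recorded contributes 12 months without an event. An AF recurrence found only by the Holter is dated near 12 months, whenever it began.

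**3. What one Holter can find (assumed: episodes at random, constant rate r per month).** P(at least one in 48 hours) = 1 - exp(-r x 2/30.4).
- r = 1: 6%
- r = 4: 23%
- r = 8: 41%

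**4. Upward bias (assumed p and s).** Let p be true 12-month recurrence and s the share of recurrences recorded. With complete follow-up and no false positives, apparent freedom = 1 - p x s. For p = 30%, true freedom is 70%:

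| s | apparent freedom |
|---|---|
| 30% | 91% |
| 50% | 85% |
| 70% | 79% |
| 95% | 71.5% |

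**5. Artificial difference between groups (assumed).** Let w be the share of device carriers, with 95% of recurrences recorded in carriers and s0 in the others. Apparent freedom = 1 - p x [0.95w + s0(1 - w)]. Take p = 40% in both groups, so true freedom is 60%:

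| s0 | w = 10% | w = 50% | difference |
|---|---|---|---|
| 40% | 1 - 0.40 x 0.455 = 81.8% | 1 - 0.40 x 0.675 = 73.0% | 8.8 points |
| 70% | 1 - 0.40 x 0.725 = 71.0% | 1 - 0.40 x 0.825 = 67.0% | 4.0 points |

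Equivalently, the difference is p x (0.50 - 0.10) x (0.95 - s0). Over p = 20-40% and s0 = 30-70% it runs from 0.20 x 0.40 x 0.25 = 2 points to 0.40 x 0.40 x 0.65 = 10.4 points.

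**The case against.** **Device events are not shut out.** A reader might infer from the note that device data enter only when the Sponsor asks. The documents do not support that. The following paragraph calls for arrhythmia documentation, including session records, to be submitted where applicable; Appendix C counts ICD, CRT and monitor recordings; and each visit collects ICD-treated ventricular episodes. Episodes known to the site enter without a request. What is discretionary is systematic retrieval. The documentation rule covers arrhythmias that were found; it does not ask for negative recordings or show who was never recorded.

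**The study is descriptive.** No hypothesis is tested, no subgroup is pre-specified, and section 7.1.1 defines no contrast by center or usage. This stands: no error rate or sample size is affected. But a descriptive comparison under the third objective is exposed to the same distortion.

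**Local recording may be good.** Table 3 lists study-specific tests only, the visits are in-clinic, and routine ECGs may be done. The CRFs are under separate cover (Appendix E) and may capture monitoring. Neither can be excluded. Even so, the analysis section makes no use of such information.

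**The size could be overstated.** On the inputs of step 5, comparing all carriers with no carriers gives observed recurrence of 0.40 x 0.95 = 38% against 16-28%, a gap of 10-22 points. A reader might take that as the likely distortion between centers or usage patterns. The documents give no device prevalence to support it, and real groups would be mixed.

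**Curves by device status would not isolate detection.** This is right. Section 3 ties ICDs to ventricular arrhythmia and structural heart disease, so device status also marks underlying disease.

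**Conclusion.** The concern holds as a point about ascertainment. The event must be documented, the protocol schedules one short recording for one arrhythmia group, systematic device retrieval has no rule, and subjects with no recorded event count as event-free to last follow-up regardless of recording. As written, the estimate is freedom from *documented* recurrence. It overstates true freedom wherever recurrences are missed, and does so unequally between subjects with and without continuous monitoring.

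The amount cannot be derived from the documents. On the assumptions in step 5, groups with 50% and 10% device carriers would differ by about 4-9 points with no true difference, or 2-10 points over the wider range. These figures show that the effect can matter; they do not estimate it. The documents do not show that device data depend wholly on the Sponsor, that subjects in fact go unrecorded, or that requests would be selective. The change is a cheap improvement.

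**What to change.** 1. **Device data.** Replace the optional request with a uniform rule: stored arrhythmia data are requested for every subject with an implanted device at the 6- and 12-month visits, regardless of outcome or system usage. This removes discretion but can widen the detection gap, because it raises detection only in carriers. It should be paired with items 2 and 3.
2. **Data capture.** If the CRFs do not already do so, record implanted-device status at baseline and, at each follow-up visit, the type and date of every rhythm recording since the last visit, including negative ones. Collect this prospectively, since it may be hard to recover later.
3. **Section 7.1.1.** Label the endpoint *freedom from documented recurrence*. Report the share of subjects with no post-procedure recording and the type of monitoring received, overall and by treated arrhythmia. Add a sensitivity analysis censoring at the last rhythm recording. Curves by baseline device status may be shown within treated arrhythmia as description only, not as a measure of detection bias.

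**Cost.** No patient procedure is added, consistent with section 8. The work is a few form fields, some data retrieval and extra tables. The sensitivity analysis has limits: it is conservative where symptoms trigger recording, it drops subjects with no recording, and it changes little for AF subjects who complete the 12-month Holter. It should stay secondary.
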